### 4.3 Intervention

#### PET scan protocol

- Fifteen (15) patients with newly diagnosed or recurrent gliomas, deemed appropriate for this scan by the investigator on the basis of imaging studies and surgical management considerations, will undergo the FLT-PET study for purposes of collecting pilot data (in compliance with RDRC regulations).
- All studies will be performed using a dedicated PET/CT, which integrates a dedicated PET scanner and a spiral CT with proprietary fusion software. Images are acquired with the patient in the fasted

IRB  
PB

Amended: 12/27/11

**Memorial Sloan-Kettering Cancer Center  
IRB Protocol**

**IRB#: 09-060 A(4)**

state (about four to six hours), but water for hydration is allowed. A low dose spiral CT is performed first, followed by acquisition of PET images (emission images only), of the brain. Attenuation correction of the PET/CT images is performed using the CT data. PET, CT and fusion images are displayed on a standard workstation.

- A IV catheter will be placed in a superficial hand or arm vein for administration of  $^{18}\text{F}$ -FLT (approximately 370 MBq), prepared by the MSKCC Radiochemistry Core Facility. A second venous catheter will be placed in the opposite hand or arm for venous blood sampling. If a central venous catheter is present, it will be used for blood sampling or radiopharmaceutical administration, and only a single venous catheter will be placed. Sequential blood samples may be obtained following  $^{18}\text{F}$ -FLT infusion for assaying whole blood and plasma radioactivity. All catheters will be removed at the end of the day.
- Dynamic PET/CT images of the brain will be acquired for up to 1-hr on a dedicated PET/CT machine, with image acquisition starting immediately after injection using the following sequence: 6 frames of 30sec, 7 frames of 1-minute, then 10 frames of 5-minutes.
- The intravenous line will be removed at the end of the study.
  - Venous blood samples (up to four) may be drawn from a vein in the arm opposite to that used to inject FLT by research staff. A single sample (approximately 3 milliliters) will be acquired at the end of the study (i.e., 60 min) for calibrating the FLT TAC, with the option to perform additional blood sampling (i.e., 15, 30, 45 min post-injection) for improving estimates of pharmacokinetic parameters.  $^{18}\text{F}$  radioactivity in the  $^{18}\text{F}$ -FLT blood/plasma samples will be measured by research staff.
  - Dynamic FLT scans will be reconstructed by both filtered back projection and iterative reconstruction in order to check for quantitative accuracy at the smaller time segments immediately post injection.
  - $^{18}\text{F}$ -FLT PET and CT examinations will be fused using a Vector-Vision® cranial navigation software (BrainLab AG, Heimstetten, Germany), after being transferred to a commercial workstation, BrainLab 1 (BrainLab AG).
  - The  $^{18}\text{F}$ -FLT PET-CT and baseline MRI studies will be uploaded onto BrainLab 1 and co-registered by the neuroradiologist using Vector-Vision® cranial navigation software. This will not be done in the operating room. The PET and MR image sets will be co-registered by applying the 3D rigid transformation (translations/rotations) to the PET image set, which aligns the CT image set of the PET-CT study and the MR image set.
  - The operating neurosurgeon will be blinded to the pre-operative PET study, and planned tumor resection volume will be pre-determined solely on the basis of anatomic MRI per routine. Preoperative MRI images will be uploaded to the BrainLAB VectorVision® neuronavigation

Memorial Sloan-Kettering Cancer Center  
IRB Protocol

IRB#: 09-060 A(4)

system, a frameless stereotaxy and image-guided surgical navigation system integrated with the Intraoperative MRI suite.

- On co-registered PET-MRI scans and prior to surgical resection, up to four prescribed ROIs within the planned resection volume will be marked for potential targeted biopsy by two neuroradiologists and a nuclear medicine attending, blinded to the surgical planning. These ROIs will be selected based on heterogeneity of PET and MRI imaging characteristics (e.g., high  $^{18}\text{F}$ -FLT uptake/no enhancement; low  $^{18}\text{F}$ -FLT uptake/enhancement). Fused images containing the marked biopsy sites will be uploaded to the BrainLAB VectorVision® neuronavigation system for viewing by the neurosurgeon in the operating room. As noted above, however, the operative plan, in terms of the tumor resection volume, will not be guided by decisions regarding sites of potential biopsy selected on the co-registered FLT PET-MRI study.
- ROI analyses for determination of tracer uptake measurements and the generation of time-activity curves for blood and tumor will be performed on an AW Workstation (GE Healthcare) that runs the Voxulus™ software module for voxel-based pharmacokinetic modeling. Voxel-based pharmacokinetic modeling, traditional ROI-based pharmacokinetic modeling (*SAAM II* program), and static uptake determinations will all be performed on this workstation. The information derived from these analyses will not be used for surgical planning or uploaded for use in the operating room.
- Non-invasive input functions for blood will be obtained non-invasively using post-injection region-of-interest measurements of the superior sagittal sinus. These measurements will be compared with arterial blood activity-concentrations from an image containing the internal carotid artery, and will be calibrated using the measurement of a single intravenous blood sample acquired at one post-injection time point. If additional blood sampling (i.e., 15, 30, 45 min post-injection) has been acquired, these measurements will be compared with non-invasively derived values and used to improve estimates of pharmacokinetic parameters.
- Surgical resection and tissue specimen acquisition will take place with frameless stereotactic tracking of resection location and updated by intraoperative MRI.
- The radiation dose from the FLT studies was calculated based on published data. Given a realistic 1- hour voiding interval, the target organ is the liver, receiving a dose of 0.168 rad/mCi, corresponding to 1.68 rad/10mCi. This is below the 5 rad single organ permissible dose. Total body dose is calculated at 0.046 rad/mCi, and 0.46 rad for a 10 mCi injection, the maximum dose that will be used (see Table below). With a 1 hour voiding interval, the dose to the urinary bladder wall will be 0.146 rad/mCi. Recent CT dosimetry literature quotes a dose of 0.9 rad/single organ from a typical CT scan, performed for the purpose of PET attenuation correction on a PET-CT scanner. The diagnostic protocol described here will not exceed the permissible limit of 5 rad/organ/single study and will also remain below the maximal permissible dose acceptable to the radioactive drug research.

**Memorial Sloan-Kettering Cancer Center  
IRB Protocol**

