## 1.1 PROTOCOL SUMMARY AND/OR SCHEMA

This is a baseline feasibility study using fluorine-18-labeled fluorothymidine ( $^{18}\text{F}$ -FLT), a proliferation tracer, and highly focal MR image-guided biopsy to evaluate whether characteristic metabolic/MR imaging findings can be linked to distinct molecular phenotypes and improve our understanding of the molecular and pathological heterogeneity within individual tumors. In addition, this study will assess the feasibility of voxel-wise estimation of proliferation and tracer delivery from overall FLT uptake assessments, as against traditional ROI-based pharmacokinetic approaches. The quantitative accuracy of these parametric images will be investigated through comparison of histologic determinations of tumor cell proliferation, CD31 expression, and gene expression differences, obtained at different biopsy locations, with the PET-MRI imaging features at those same locations. The results of these studies will lay the groundwork for larger prospective studies assessing  $^{18}\text{F}$ -FLT proliferative response in trials of targeted therapy, relating estimates of proliferation with prognosis, survival, and clinical outcome.

Please note that all patients entered on this protocol will undergo the standard of care for their brain tumor. The information obtained from the use of  $^{18}\text{F}$ -FLT PET scans will NOT be used to guide patients' surgical planning on this protocol. Since FLT PET is considered investigational, subjects enrolled in this protocol will only undergo FLT PET scans under an FDA-approved institutional IND (#104742).

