#### 4.1 OVERVIEW OF STUDY DESIGN/INTERVENTION

##### 4.2 Design

This is a two-year open-label pilot study at Memorial Sloan Kettering Cancer Center that will enroll 15 patients with initial presentation of presumptive glioblastoma based on prior radiographic studies for  $^{18}\text{F}$ -FLT PET imaging correlation with histologic and molecular markers. Standard baseline pretreatment MRI studies will be obtained following injection of gadolinium (GdDTPA) and a pre-surgical dynamic  $^{18}\text{F}$ -FLT PET study with CT for attenuation correction will be performed on Day 1. Surgical resection will be performed within a 7 day period of these imaging studies. The planned tumor resection volume will be pre-determined by the operating neurosurgeon on the basis of anatomic/functional MRI per routine, and blinded to the results of the preoperative PET study. Two neuroradiologists (Drs. [name] and [name]) and a nuclear medicine attending ([name]), blinded to the surgical planning, will independently identify “patterns of interest” or sites of heterogeneity within the tumor on co-registered PET-MRI scans for targeted biopsy. Fused images containing the marked biopsy sites will be uploaded to the BrainLAB VectorVision® neuronavigation system for viewing by the neurosurgeon in the operating room. Selected targeted sites will be marked as potential biopsy targets if they are: (1) contained within the pre-determined planned tumor resection volume, (2) over  $1\text{cm}^3$ , and (3) abnormal on intraoperative visualization. Surgical resection will take place per routine with frameless stereotactic tracking of resection location, updated by intraoperative MRI (iMRI, 1.5T Siemens magnet). As target sites are encountered, up to 1gm of tumor will be marked as a separate biopsy specimen and flash frozen in liquid nitrogen. Biopsy specimens will be taken only after adequate material has been acquired for routine pathology. Prior to histopathologic and molecular characterization, biopsy specimens will be inspected by the pathologist to insure adequacy of tumor tissue sampling and to definitively diagnose tumor. Histopathologic and molecular characterization of the biopsied tumors will be performed, specifically immunohistochemical staining for MIB-1, in addition to gene expression profiling. Data analysis will include physician interpretation of brain MRI and PET scans, volumetric region-of-interest (ROI) analyses of tumor and contralateral brain, generation of  $^{18}\text{F}$ -FLT time activity curves (TACs) and steady-state SUVs, non-invasive determination of plasma TACs (venous and arterial input curves), as well as voxel-based and ROI-based pharmacokinetic modeling. *Periodic meetings will be held to discuss issues related to data acquisition, collection, and analysis, as well as to discuss the imaging and histopathology data.*

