Post-hoc mapping of biopsy sites into presurgical image coordinates will determine which samples were in fact within the target ROI. The primary limitation of the approach is that it relies on the surgeon's estimation of where an ROI has shifted intraoperatively in order to direct biopsies: it is possible that some ROIs may be missed or deemed to be outside the resection volume and hence unavailable for biopsy. However, the minimum proposed ROI size of 1.0 cm^3 is within the range of intraoperative accuracy routinely used by neurosurgeons during resection to avoid vascular and neuroanatomic structures. Therefore it is anticipated that at least one specimen be taken from the vicinity of the ROI, as judged by the surgeon; it will be established post-hoc as being accurately mapped to within an ROI. Acquiring tissue from surgically exposed tumor, as proposed here, avoids the significant risk of parenchymal bleeding from deep needle biopsy. If difficulties are encountered implementing the above plan, needle biopsy sampling through an initial minimal surgical exposure will be employed under a separate IRB-approved protocol.

Biopsy specimens will be acquired for research purposes after pathologic specimens are submitted for the patient per routine by neurosurgery. A minimum of 1.0 g of biopsy tissue will be acquired per patient for research purposes, as the priority for the study is histologic validation. We will ensure that as much tissue as possible is sent for histology, aiming for roughly half of the specimens to be further processed as frozen sections for research purposes.

Biopsy specimens will be frozen immediately in liquid nitrogen and stored at -80 °C until later use. All biopsy cores will be divided in half, with one half of the frozen tissue specimen sectioned for RNA and DNA expression analysis, and the remaining half processed as a formalin-fixed paraffin-embedded (FFPE) specimen for immunohistochemistry by fixing the tissue in 10% neutral buffered formalin for 2 days, followed by paraffin embedding. Tissue markers for tumor cell proliferation (MIB-1) and

**IRB  
PB**

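### The neurosurgeon's blind to FLT-PET protects the resection volume but not the research sampling, because fused PET-MRI is uploaded for viewing in the operating room

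*Combined protocol and SAP*

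**What the plan says.** Section 4.3 (Intervention, PET scan protocol) has this sentence: "The operating neurosurgeon will be blinded to the pre-operative PET study". The following bullet has the readers mark up to four targets on the co-registered PET-MRI and continues: "Fused images containing the marked biopsy sites will be uploaded to the BrainLAB VectorVision® neuronavigation system for viewing by the neurosurgeon" in the operating room. Section 4.2 (Design) describes the same upload. Directly after the upload sentence, section 4.3 adds a limit: "the operative plan, in terms of the tumor resection volume, will not be guided by decisions regarding sites of potential biopsy".

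Elsewhere the blind is worded more narrowly. Schema item c and section 4.2 attach it to fixing the planned resection volume. The Primary Aim Study Design in section 4.2 has that volume contoured on anatomic MRI before the PET-MRI is loaded. The Protocol Summary says that FLT-PET information "will NOT be used to guide patients' surgical planning on this protocol".

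The surgeon keeps discretion over the research tissue. Under section 4.2, a marked site becomes a biopsy target only if, among other conditions, it is "abnormal on intraoperative visualization". The Primary Aim Study Design has several pieces collected near each region of interest (ROI) and concedes of the approach that "it relies on the surgeon's estimation of where an ROI has shifted intraoperatively in order to direct biopsies". Samples are then mapped back to the presurgical images and accepted or rejected by location.

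**The concern.** The primary aim relates FLT kinetic parameters to Ki-67 and CD31 at matched sites. Secondary Aim #2 asks whether SUV or k3 tracks Ki-67 better. Both need the tissue at a given site to be chosen without regard to how hot that site is on FLT.

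A surgeon who can see uptake may look harder for tumour-like tissue at a hot target, or more readily judge a cold target unremarkable and leave it unsampled. Either behaviour makes the histology depend on the PET through the sampling rather than through biology. The random-effects or GEE models in section 11.0 deal with several observations per patient; they do not correct for this. Finding the target requires its position, and none of the three judgements needs its FLT intensity.

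**Working it through.** The plan gives no figure on this point to reproduce, so the check is mainly a comparison of texts.

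**1. What the blind covers**

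| Step | Surgeon masked to PET? | Source |
|---|---|---|
| Contouring the resection volume | Yes; done on anatomic MRI before PET-MRI is loaded | Schema c; 4.2; 4.3 |
| Viewing marked sites in the operating room | No; fused images uploaded | 4.2; 4.3 |
| Judging a target abnormal | Not stated | 4.2 |
| Estimating where the ROI has shifted | Not stated | 4.2, Primary Aim |
| Choosing pieces near the ROI | Not stated | 4.2, Primary Aim |

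The unqualified sentence in 4.3 conflicts with the second row. The limiting sentence in 4.3 resolves the conflict for the resection volume only.

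**2. What mapping can detect**

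ROIs are at least 1 cm³, and localization accuracy is given as about 1 cm³ (4.2). Mapping can reject a piece taken outside the ROI. It cannot tell a piece chosen for its appearance from any other piece inside the same ROI, and it has nothing to say about a target that was never sampled.

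**3. Two mechanisms to keep apart**

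- *Choosing sites by PET value*, which is the intended design. In a bivariate-normal simulation (2,000,000 draws, true correlation 0.60), taking sites only from the upper and lower thirds of PET values raises the correlation to 0.67 but leaves the regression slope at 0.60.
- *Choosing tissue within a site differently by PET level*. This shifts mean Ki-67 at a given FLT value, so it biases the slope as well as the correlation.

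**4. Illustration of the second mechanism (assumed inputs)**

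Assume no true association and equal numbers of high- and low-FLT sites. At high-FLT sites the most abnormal-looking of m = 2 or 3 pieces is taken; at low-FLT sites any piece is taken. Appearance correlates ρ = 0.3 or 0.5 with Ki-67. None of these inputs is in the protocol.

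The expected maximum of m standard normals is 0.564 (m = 2) or 0.846 (m = 3). The shift is d = ρ × that maximum, and r ≈ d/√(d² + 4), taking the within-group SD as 1.

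- m = 2, ρ = 0.3: d = 0.169; r = 0.169/√4.029 = 0.08
- m = 2, ρ = 0.5: d = 0.282; r = 0.282/√4.080 = 0.14
- m = 3, ρ = 0.3: d = 0.254; r = 0.254/√4.065 = 0.13
- m = 3, ρ = 0.5: d = 0.423; r = 0.423/√4.179 = 0.21

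A simulation with 200,000 draws per setting gives the same four correlations.

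**5. Scale**

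Section 11.0 expects 15 patients with two observations each on average, or 30. If these were independent, the standard error of r near zero would be about 1/√29 = 0.19. The illustrated bias is therefore about 0.4 to 1.1 standard errors (0.08/0.19 to 0.21/0.19).

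**6. Loss of cold targets**

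If the cold targets left unsampled are those with low Ki-67, the remaining cold sites look more proliferative and the association is weakened. If they include cold tissue that looks ordinary but proliferates, the association is strengthened. The direction is open.

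**The case against.** The strongest reply is that the protocol foresaw the tension. The Schema and section 4.2 tie the blind to the resection volume, the order of work protects it, and section 4.3 repeats the limit straight after describing the upload. This stands. A reader might infer that the blind on resection is broken, or that PET is steering the operation. The documents do not support either reading, because the statements on surgical guidance concern planning and volume.

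Nor does any section promise sampling independent of PET. Targets are deliberately chosen for concordant or discordant PET and MRI appearance, and that dependence would remain with neutral outlines. This also stands, which is why the point is limited to tissue choice within targets and to their retention.

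Three further safeguards exist: location mapping, a pathologist's adequacy check, and the rule in 4.3 that kinetic and static uptake analyses stay out of the operating room. The last means that the surgeon would see at most an uptake image, not K1 to k4 maps. The display settings are not described, so visible FLT intensity at each judgement is a plausible inference and not a stated fact. These safeguards narrow the concern, but none prevents uptake-dependent choice inside an ROI.

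The numerical scenario is fairly criticised. The plan collects several pieces per ROI and applies the visual criterion to every target, so complete asymmetry between hot and cold sites is a construction. Section 11.0 also calls all analyses exploratory.

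**Conclusion.** The point holds in a limited form and is a cheap improvement. The unqualified blinding sentence in 4.3 and the upload sentences in 4.2 and 4.3 need reconciling. As written, nothing stops visible FLT uptake from influencing which tissue within a target is taken, or whether a target is sampled. That matters for the primary aim and for the SUV-versus-k3 comparison in Secondary Aim #2, which is descriptive and could be swayed by small differences.

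The size and direction of any bias are unknown. A reader might take 0.08 to 0.21 as the expected inflation. It is not: it rests on an assumed asymmetry and an assumed link between appearance and Ki-67, and it leaves out the loss of cold targets, which could push either way. The conclusion assumes that the fused view shows PET uptake, as the term suggests.

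**What to change.** - In sections 4.2 and 4.3, replace the fused-image upload with ROI outlines on the anatomic MRI, labelled Target 1 to 4, without the PET overlay or any FLT class.
- Reword the blinding sentence in 4.3 to give its scope and end: the surgeon stays masked to PET until the last research specimen is labelled.
- For each coded target, record whether it was judged abnormal and whether it was sampled. Tabulate losses by FLT class.

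The cost is a wording change, a different export to the navigation system and a short log, with no added staff or procedure. The surgeon loses an overlay that the protocol says does not guide the resection volume. Masking would be only partial, because enhancement on the MRI may hint at the class. The pairings in the Primary Aim Study Design list non-enhancing targets only with increased uptake (that pairing is printed twice, perhaps a slip), and the examples in 4.3 pair high uptake with no enhancement.

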**IRB#: 09-060 A(4)**

- **F18-Fluorothymidine (FLT) Patient Dosimetry**  
Dosimetry for one PET FLT - CT scan

Target Organ	Absorbed Dose		
	1 FLT PET-CT scans		
	0.9 rad  + 10 mCi F18-FLT		
	F18-FLT 		
	rad/mCi	rad/10 mCi	rad
One FLT PET-CT scan			
Adrenals	0.077	0.766	1.67
Bone Surfaces	0.058	0.585	1.48
Brain	0.013	0.125	1.03
Breasts	0.031	0.310	1.21
Heart Wall	0.062	0.618	1.52
Kidneys	0.132	1.317	2.22
Large Intestine - Lower Wall	0.048	0.477	1.38
Large Intestine - Upper Wall	0.046	0.459	1.36
Liver	0.168	1.680	2.58
Lungs	0.037	0.374	1.27
Pancreas	0.085	0.851	1.75
Red Marrow	0.089	0.888	1.79
Small Intestine	0.053	0.525	1.43
Stomach Wall	0.052	0.522	1.42
Testes	0.049	0.488	1.39
Thyroid	0.038	0.385	1.28
Urinary Bladder Wall			
45-min Voiding Interval	0.110	1.098	2.00
1-hr Voiding Interval	0.146	1.463	2.36
1.5-hr Voiding Interval	0.220	2.195	3.10
2-hr Voiding Interval	0.293	2.927	3.83

**5.1 CRITERIA FOR SUBJECT ELIGIBILITY**

The patient population will be comprised of patients with newly-diagnosed or recurrent high grade gliomas.

**5.2 Subject Inclusion Criteria**

5.1.1. Age  $\geq$  18 years old.

5.1.2. Radiographic appearance of a lesion presumed to be high-grade glioma.

Amended: 12/27/11

**Memorial Sloan-Kettering Cancer Center  
IRB Protocol**

**IRB#: 09-060 A(4)**

5.1.3. Planned surgical resection.

**5.2 Subject Exclusion Criteria**

5.2.1. Pregnant (confirmed by serum b-HCG in women of reproductive age) or breast feeding

5.2.2 Patients with other active malignancies or prior treatment for non-CNS malignancies.

